#### **4.6 Adverse Event Reporting**

Detailed information concerning adverse events will be collected and evaluated throughout the conduct of the protocol. Adverse events will be reported to the Institutional Review Board per policy.

## **4.7 Study Outcome Measures**

### **4.7.1 Primary Outcome**

The primary outcome is complete platelet inhibition by aspirin. This will be evaluated with measured maternal serum thromboxane levels at randomization, in the second trimester, and on admission to labor and delivery.

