### **1.2 Study Hypothesis:**

In women, taking 162mg of aspirin daily has improved inhibition of platelet function, compared to a dose of 81mg daily.

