### **3. Study Design**

#### **3.1 Primary Research Question**

This randomized trial will address the primary research question:

In women, does taking 162mg of aspirin daily, starting between 12 and 16 weeks of gestation, result in a lower incidence of aspirin resistance, when compared to a daily dose of 81mg?

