## **5. Statistical Considerations**

### **5.1 Data Relevant to the Primary Outcome**

As discussed in the background, pregnancy is associated with an increased prevalence of aspirin resistance. The literature suggests that women have an aspirin resistance rate of 26% with low-dose aspirin, compared to 20.5% in non-pregnant women.

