### **5.2 Sample Size and Power**

For this calculation, we performed a power analysis comparing patients taking a total of 81mg of aspirin daily, to patients taking 162mg of aspirin daily.

We predicted that taking 162mg of aspirin daily will be associated with a 35% reduction in aspirin resistance. Assuming a two-sided alpha of 0.05, it is estimated that 128 women/group (256 total) would provide 80% power to detect the above described reductions in the frequency of aspirin resistance in the 2 groups. Assuming an approximately 30% rate of drop out and loss to follow up, we will collect data on a total of 400 patients to achieve the required statistical power. Patients will be randomized in a 1:1 ratio.

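### Serum thromboxane is measured as a level before and during treatment, but no comparison of levels between doses is pre-specified to support a yes/no primary comparison that lacks its stated 80% power

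*Combined protocol and SAP*

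**What the plan says.** The hypothesis in 1.2 is graded: "taking 162mg of aspirin daily has improved inhibition of platelet function, compared to a dose of 81mg daily". The primary question in 3.1 is a yes/no one, whether the higher dose will "result in a lower incidence of aspirin resistance, when compared to a daily dose of 81mg". Section 4.7.1 then defines the endpoint through a quantitative assay: "The primary outcome is complete platelet inhibition by aspirin. This will be evaluated with measured maternal serum thromboxane levels", taken at randomization, in the second trimester and on admission for delivery. Sections 4.3, 4.4 and 4.5 schedule the matching blood draws, so each woman is to have a baseline level and on-treatment levels.

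Section 5 holds a background rate (5.1: "women have an aspirin resistance rate of 26% with low-dose aspirin, compared to 20.5% in non-pregnant women") and a sample-size calculation. Section 5.2 predicts that "taking 162mg of aspirin daily will be associated with a 35% reduction in aspirin resistance" and says of 128 women per group that they give "80% power to detect the above described reductions in the frequency of aspirin resistance in the 2 groups". It plans 400 women to allow for about 30% loss. No analysis method is stated. The secondary outcomes in 4.7.2 and 4.7.3 include other biomarkers but no thromboxane comparison.

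**The concern.** The measurement that tests the graded hypothesis most directly is collected, but nothing says it will be compared between doses. The only comparison with any statistical specification is the frequency of resistance. If that comparison is weaker than the protocol believes, the trial could report no difference in resistance while thromboxane is lower on 162mg. Any analysis of levels would then be post hoc. The documents also give no thromboxane cut-off for resistance, so a pre-specified comparison of levels would be the one result that a later choice of cut-off cannot change.

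**Working it through.** **Inputs.** Control rate 26% (5.1), or about 30% (2.2). Reduction 35% (5.2), read as relative because an absolute fall of 35 points from 26% or 30% is impossible. Two-sided alpha 0.05, 1:1 allocation, 128 per group (5.2). Evaluable after loss: 400 × 0.70 = 280, or 140 per group.

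**1. The protocol's own figure.** p1 = 0.26, p2 = 0.26 × 0.65 = 0.169, difference 0.091, mean rate 0.2145.

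n per group = [1.960·√(2 × 0.2145 × 0.7855) + 0.8416·√(0.26 × 0.74 + 0.169 × 0.831)]² / 0.091² = (1.1378 + 0.4856)² / 0.008281 ≈ 318.2, so 319.

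The stated 128 does not reproduce. A continuity correction gives 340, a one-sided test 251, the arcsine method 316. From 30% to 19.5% the answer is 264. A figure near 128 needs a control rate near 50% (124 per group), or a reduction of about 53% from 26%.

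**2. Power of the yes/no comparison.** Power = Φ{[0.091 − 1.960·√(2 × 0.2145 × 0.7855/n)] / √[(0.1924 + 0.1404)/n]}. At n = 128: Φ[(0.0910 − 0.1006)/0.0510] = Φ(−0.188) = 42.6%. Exact enumeration of the chi-square test also gives 42.6%.

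| Control rate | 128/group | 140/group | 200/group (no loss) |
|---|---|---|---|
| 26% | 42.6% | 45.8% | 60.2% |
| 30% | 49.5% | 53.0% | 68.3% |

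**3. Power of a comparison of levels.** The documents give no mean, SD or cut-off for thromboxane, so everything here is assumption. Each case below is for 128 per group without baseline adjustment.

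- *Normal on the log scale, equal SDs, pure shift, tail rates 26% and 16.9%.* Shift = 0.9581 − 0.6433 = 0.315 SD. Power = Φ(0.315 × √64 − 1.960) = Φ(0.558) = 71.2% (70.8% by noncentral t). At 140 per group it is 75.0%.
- *Same tail rates, unequal SDs.* With the 81mg-arm SD at 1 and the 162mg-arm SD at s, the mean shift is s × 0.9581 − 0.6433 and its standard error is √[(1 + s²)/128]. For s = 0.8: 0.123/0.113, power about 19%. For s = 0.9: 0.219/0.119, about 45%. For s = 1.2: 0.506/0.138, about 95% to 96%.
- *Two distinct classes, where the dose changes only the resistant share (26% to 16.9%).* Simulated t-test power is 20%, 28% and 33% for classes 2, 3 and 4 SD apart. The yes/no test has 43% if class is read without error. With a cut-off midway between classes 4 SD apart it has 38%. At 2 SD apart, misclassification brings the rates to 0.26 × 0.841 + 0.74 × 0.159 = 33.6% and 0.169 × 0.841 + 0.831 × 0.159 = 27.4%, and power to about 19%, level with the t test.

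**4. Baseline adjustment.** In the equal-SD case, an assumed baseline correlation of 0.3 or 0.5 raises the 71% to 75% or 83%. The documents give no correlation.

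**The case against.** The strongest objection concerns cause. A reader might infer that reducing thromboxane to yes/no is what leaves 43% power. The documents do not support that: 128 per group does not follow from the protocol's own rates, and a yes/no trial of 319 per group would have 80%. This objection stands, and the two issues must be kept apart.

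A reader might also infer that comparing levels would give 71% power, or that dichotomising loses information at any cut-off. Neither is supported. The 71% needs equal SDs and a pure shift. A narrower spread on 162mg removes or reverses the advantage, and so do well-separated classes. The protocol speaks of resistance as a state that some women are in (2.2, 5.1), so the two-class picture cannot be set aside.

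It can also be said that the protocol does not strictly choose two proportions. It names no analysis, and 1.1, 1.2 and 4.7.1 leave room for levels. That is fair, but what is missing is the pre-specification itself.

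Section 2.2 further cites a fall from about 30% to about 5%, for which 128 per group gives over 99% power. Section 5.2 does not size on that contrast, so it does not rescue the stated calculation.

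Finally, a supportive analysis leaves primary power unchanged. That is true, and it is why 5.2 needs its own correction. None of these objections counts against adding the analysis, because the resistance comparison stays in place.

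**Conclusion.** The point holds in a limited form. Levels are collected at baseline and on treatment, the hypothesis is graded, and no comparison of levels between doses is pre-specified. This matters more because the yes/no comparison has about 43% to 46% power at 26% resistance, or about 50% to 53% at 30%, against the stated 80%. Those figures rest only on the protocol's rates and the relative reading of 35%.

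How much power a comparison of levels would add is not known. From the documents, anything from about 19% to 95% at 128 per group is compatible with the same resistance rates, and 71% is one illustration within that range. A reader might conclude that levels should replace resistance as primary. The documents do not settle that: without SD data it is a trade-off, and even the equal-SD case stays below 80% at 128 or 140 per group before baseline adjustment.

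**What to change.** In 5.2, restate the power of the resistance comparison from the rates actually assumed, or re-size the trial.

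In 4.7 and section 5, keep the resistance proportion as primary and add a first-ranked supportive analysis of the primary objective:

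- Estimate: the 162mg:81mg ratio of geometric mean serum thromboxane, with 95% confidence interval.
- Model: linear on the log scale, at the same named on-treatment time point as the resistance comparison, adjusted for the baseline thromboxane already collected.
- Values below the assay limit: treated as left-censored, or a rank analysis used instead.
- Reporting: alongside the resistance proportions, whatever their p-value.
- Power: any figure quoted should come from real SD data and be labelled conditional on the assumed distribution.

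The supportive analysis costs protocol wording and one model, with no new women, visits or tubes. The downside is one more reported comparison, and a ratio of levels needs a sentence of clinical interpretation.

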### **4.7.2 Maternal Secondary Outcomes**

- Diagnosis of eclampsia, HELLP, atypical HELLP, preeclampsia, superimposed preeclampsia or antepartum gestational hypertension, using standard American College of Obstetricians and Gynecologists criteria, during the pregnancy or up to 30 days postpartum;
- Placental growth factor levels and soluble fms-like tyrosine kinase 1 levels, to evaluate whether the values are predictive of aspirin resistance, as the ratio of both values has been validated as a predictor of preeclampsia;
- Aspirin-triggered 15-epi-lipoxins;
- Gestational diabetes by oral GTT criteria performed after randomization;
- Preterm birth < 34 weeks and < 37 weeks, both spontaneous and indicated;
- Operative vaginal delivery and cesarean delivery;
- Estimated and quantitative blood loss;
- Blood transfusion;
- Epidural hematoma;
- Maternal morbidity and adverse maternal outcomes, including venous thromboembolism, peripartum cardiomyopathy, massive transfusion and postpartum hemorrhage, ICU admission, and maternal death.

The maternal plasma exosome proteome profile

#### **4.7.3 Neonatal Secondary Outcomes**

- Antepartum, intrapartum, or neonatal death
- Intubation, continuous positive airway pressure (CPAP) or high-flow nasal cannula (HFNC) for ventilation or cardiopulmonary resuscitation within first 72 hours
- Birth weight
- Neonatal encephalopathy as defined by the NICHD Neonatal Research Network criteria
- Seizures
- Shoulder dystocia
- Birth trauma (bone fractures, brachial plexus palsy, other neurologic injury, retinal hemorrhage, or facial nerve palsy)
- Intracranial hemorrhage (intraventricular hemorrhage, subgaleal hematoma, subdural hematoma, or subarachnoid hematoma)
- Hyperbilirubinemia requiring phototherapy or exchange transfusion
- Hypoglycemia (glucose < 35 mg/dl) requiring IV therapy
- NICU admission

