#### **3.2 Secondary Research Questions**

Secondary research questions that this study will address are whether in pregnant women, a daily aspirin dose of 162mg, compared to a daily dose of 81mg, starting between 12 and 16 weeks of gestation, will decrease the risk of:

- Preeclampsia;
- Gestational hypertension;
- Gestational diabetes;
- Composite maternal cardiovascular outcome;
- Composite maternal morbidity, including postpartum hemorrhage;
- Operative vaginal delivery, cesarean delivery;
- Neonatal morbidity and mortality.

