#### **3.3 Design Summary**

This study is a non-blinded prospective randomized trial of pregnant women with a singleton pregnancy between 12 weeks 0 days and 16 weeks 0 days gestation. Participants will be randomized to receive either:

- Aspirin 81mg daily at bedtime until delivery;
- Aspirin 162mg daily at bedtime (2x 81mg tablets) until delivery;

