### **4.2 Randomization**

Patients will be randomized to taking either 81mg daily or 162mg daily of aspirin. If the patient is below 12 weeks of gestation, she will be asked to start taking the medication at 12 weeks 0 days at bedtime. If the patient is between 12 weeks 0 days and 16 weeks 0 days gestation, she will be asked to start taking the medication at bedtime on the day of enrollment. The aspirin pills will be provided to the patient on the day of randomization.

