#### 4.4 Patient Management and Follow Up

Patients will continue to receive standard prenatal care with their treating physician. Patients typically have their blood pressure and weight measured at all prenatal visits, and this information will be collected.

Patients typically have a second trimester lab draw at approximately 27 weeks of gestation. We will ask the patient to allow us to obtain additional blood tubes during the same draw, therefore not exposing the patient to added needle sticks. This will test for aspirin-triggered 15-epi-lipoxins, exosomes, thromboxane levels, placental growth factor levels and soluble fms-like tyrosine kinase 1 levels. A urine sample will also be collected on that visit, to measure urine thromboxane levels.

Study personnel will meet with participants monthly, at the time of prenatal care visits, to ascertain compliance with study agent, query for side effects or complications, and to chart abstract medical/obstetrical complications and recorded blood pressure.

All other obstetric care is at the discretion of the primary provider, including but not limited to: treatment of maternal medical comorbidities or obstetric complications, timing and frequency of antenatal ultrasound, maternal and fetal surveillance, and timing and mode of delivery.

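### The neonatal outcome labelled intracranial hemorrhage (4.7.3) includes subgaleal hematoma, a bleed outside the skull, so the label does not fit one of its four components

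*Combined protocol and SAP*

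**What the plan says.** Section 4.7.3 defines one of the neonatal secondary outcomes as "Intracranial hemorrhage (intraventricular hemorrhage, subgaleal hematoma, subdural hematoma, or subarachnoid hematoma". Any one of the four named diagnoses is enough for an infant to count.

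The item just above it in the same list is "Birth trauma (bone fractures, brachial plexus palsy, other neurologic injury, retinal hemorrhage, or facial nerve palsy". Subgaleal hematoma is not named there.

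Section 4.5 says that infant data are abstracted from charts until discharge or 30 days postpartum, whichever comes first. Section 5 covers the background rate for the primary outcome and the sample size. It says nothing about how neonatal outcomes are to be tabulated, and no section provides for adjudication or for reporting the components of this item separately.

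**The concern.** The label and the rule disagree. A reader of the results would take the row to mean bleeding inside the head, but an abstractor who follows the list would also enter infants whose only bleed is between scalp and skull.

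This deserves attention because the trial compares two doses of an antiplatelet drug (4.2: "Patients will be randomized to taking either 81mg daily or 162mg daily of aspirin"), so neonatal bleeding is a natural safety reading, and this is the only item in 4.7.3 devoted to bleeding inside the head. What is at stake is the meaning of that row: how many infants in each arm had a true intracranial bleed. The primary outcome and the conclusion on aspirin resistance are not at stake.

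**Working it through.** The plan has no figure to reproduce on this point, so the main check is of the definition.

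**Step 1: each component against the label.**

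| Component named in 4.7.3 | Site | Fits the label? |
|---|---|---|
| Intraventricular hemorrhage | inside the skull | yes |
| Subdural hematoma | inside the skull | yes |
| Subarachnoid hematoma | inside the skull | yes |
| Subgaleal hematoma | beneath the scalp aponeurosis, outside the skull | no |

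**Step 2: does anything else resolve it?** Sections 3.2, 4.5, 4.7.2, 4.7.3 and 5 contain no second definition, no category for bleeds outside the skull and no requirement to show the components separately. An infant with a subgaleal hematoma alone is therefore scored as intracranial.

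**Step 3: how large could it be?** The document gives no rate for either bleed. The rates below are assumptions, used only to show the range.

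- Births: 400 enrolled, or 256 at the required analysable number (both from 5.2).
- Assumed rate of subgaleal hematoma, s: 0.05% to 1%.
- Assumed rate of true intracranial hemorrhage, i: 0.5% to 2%.
- Expected count = births × rate.
- Share of the row that is subgaleal = s / (s + i). This treats the two groups as not overlapping. An infant with both bleeds is correctly counted, so overlap makes the misclassified share smaller.

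Expected counts over both arms:

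| | 400 births | 256 births |
|---|---|---|
| Subgaleal | 400 × 0.0005 = 0.2 to 400 × 0.01 = 4 | 0.13 to 2.56 |
| True intracranial | 400 × 0.005 = 2 to 400 × 0.02 = 8 | 1.28 to 5.12 |

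Share of the row that is subgaleal:

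- Lowest: 0.05 / (0.05 + 2) = 2%.
- Highest: 1 / (1 + 0.5) = 67%.

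The share could be negligible or large, so the range does not establish a size. The absolute count is small throughout.

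**Step 4: can the row support a comparison at all?** Take 128 infants per arm (5.2).

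- Two events, both in one arm: two-sided Fisher p = 2 × (128 × 127) / (256 × 255) = 0.50.
- Four events, all in one arm: two-sided Fisher p = 2 × (128 × 127 × 126 × 125) / (256 × 255 × 254 × 253) = 0.12.

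At these counts the item is descriptive, with or without the subgaleal cases.

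**The case against.** The strongest defence is that this is a heading that does not fit one component, and no more. The components are named, so a results table could separate them, and a subgaleal hematoma is still a bleed worth recording in a trial of antiplatelet doses. Moving it in among fractures and nerve palsies could make it less visible. This stands, and it shapes the fix: the event should stay in view as a bleed. It does not remove the mismatch, because the plan does not commit to separating the components.

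A reader might infer more than the document supports:

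- **That the rule biases the dose comparison through instrumental delivery.** Operative delivery is an outcome (4.7.2: "Operative vaginal delivery and cesarean delivery"), providers decide on "maternal and fetal surveillance, and timing and mode of delivery", and the trial is open-label (3.3: "This study is a non-blinded prospective randomized trial of pregnant women with a singleton pregnancy"). But the arms are randomized and one definition applies to both. If dose changed mode of delivery and so changed subgaleal bleeds, that would be a downstream effect of dose, not confounding. The document does not state what causes subgaleal hematoma, and the other three bleeds may also be affected by the course of delivery or by preterm birth.
- **That the protocol expects the arms to differ in operative delivery.** Section 3.2 lists "Operative vaginal delivery, cesarean delivery" under a question about whether the higher dose reduces risk. It does not predict a difference.
- **That delivery injuries in general are scored as intracranial.** Fractures, brachial plexus palsy and facial nerve palsy are in the birth-trauma item. Only subgaleal hematoma is affected.
- **That one or two reclassified infants would change the reading.** Step 4 of the working shows that a split of two against none gives p of about 0.50. No inference rests on this row.

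**Conclusion.** The point holds as an error in one outcome definition: as written, a subgaleal hematoma alone counts as an intracranial hemorrhage. This follows from the wording and from anatomy and needs no assumed rate.

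It is minor. It affects the meaning of one rare secondary outcome for which the trial is not powered. The sample size in 5.2 ("it is estimated that 128 women/group (256 total) would provide 80% power") concerns aspirin resistance and is unaffected, as is the primary outcome. The documents do not support calling it a bias between the arms. How many infants it would touch cannot be known from the document; the range of 0.2 to 4 among 400 births rests entirely on assumed rates.

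**What to change.** In 4.7.3, restrict the intracranial hemorrhage item to intraventricular, subdural and subarachnoid bleeding, and add subgaleal hematoma as its own neonatal bleeding line, tabulated by arm. An equally sound alternative is to rename the item *Intracranial or subgaleal hemorrhage* and commit to reporting each component separately by arm.

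Listing subgaleal hematoma under birth trauma is optional. That item already includes retinal hemorrhage, so it would not be out of place, but the separate line should be kept so that the bleed stays visible.

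The cost is one definition and the matching REDCap field. The same charts are abstracted and no data are lost. The only downside of the first option is a slightly smaller intracranial count; the renaming option leaves the combined count as it is.

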## **5. Statistical Considerations**

### **5.1 Data Relevant to the Primary Outcome**

As discussed in the background, pregnancy is associated with an increased prevalence of aspirin resistance. The literature suggests that women have an aspirin resistance rate of 26% with low-dose aspirin, compared to 20.5% in non-pregnant women.

### **5.2 Sample Size and Power**

For this calculation, we performed a power analysis comparing patients taking a total of 81mg of aspirin daily, to patients taking 162mg of aspirin daily.

We predicted that taking 162mg of aspirin daily will be associated with a 35% reduction in aspirin resistance. Assuming a two-sided alpha of 0.05, it is estimated that 128 women/group (256 total) would provide 80% power to detect the above described reductions in the frequency of aspirin resistance in the 2 groups. Assuming an approximately 30% rate of drop out and loss to follow up, we will collect data on a total of 400 patients to achieve the required statistical power. Patients will be randomized in a 1:1 ratio.

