### **2.2 Biological Mechanisms**

The etiology and pathogenesis of preeclampsia are multifactorial, and are characterized by an abnormal vascular response to placentation, resulting in increased vascular resistance, enhanced platelet aggregation, activation of the coagulation system, and endothelial cell dysfunction. This is thought to be at least partially the result of an increased thromboxane A2 levels, and reduced prostacyclin levels. These effects can be demonstrated as early as 13 weeks in at-risk pregnancies. Low-dose aspirin has been shown to counteract this imbalance; aspirin inhibits cyclooxygenase-1 and its thromboxane production. This explains aspirin's effectiveness as a preventative medication for preeclampsia. Treatment with 81mg of aspirin, starting between 12 and 16 weeks of gestation, is associated with an at least 8% reduction in the onset of preeclampsia during that pregnancy.

However, there is evidence to suggest that failure of low-dose aspirin in preventing preeclampsia may be related to incomplete inhibition of platelet aggregation at the recommended dosage, or "aspirin resistance". In fact, by increasing using a dose of 162mg instead of 81mg, the rate of aspirin resistance drops from approximately 30% to around 5%.

There is data to suggests that dosing aspirin at bedtime results in somewhat better morning platelet inhibition. Also, twice-daily aspirin dosing, compared to once-daily dosing, has been persistently shown in the literature to be associated with improved platelet inhibition.

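### 128 women per group does not give 80% power for a 35% reduction in aspirin resistance: from the 26% rate in section 5.1, power is about 43%

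*Combined protocol and SAP*

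**What the plan says.** Section 5.1, on data relevant to the primary outcome, reports that "women have an aspirin resistance rate of 26% with low-dose aspirin, compared to 20.5% in non-pregnant women". Section 5.2 then predicts that "162mg of aspirin daily will be associated with a 35% reduction in aspirin resistance", sets the error rate ("Assuming a two-sided alpha of 0.05"), and concludes that "it is estimated that 128 women/group (256 total) would provide 80% power to detect the above described reductions in the frequency of aspirin resistance". It allows for roughly 30% dropout and loss to follow-up, with 1:1 allocation, and says "we will collect data on a total of 400 patients to achieve the required statistical power".

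Section 5.2 does not restate the control rate, give the rate expected on 162 mg, say whether 35% is relative or absolute, or name the test.

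The background gives a different effect for the same two doses. Section 2.2 says that on moving from 81 mg to 162 mg "the rate of aspirin resistance drops from approximately 30% to around 5" per cent.

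**The concern.** Detecting a one-third relative reduction from a rate of about one quarter usually takes several hundred women per group, so 128 looks too small. This calculation is the only justification of the trial's size, and it concerns the primary research question in section 3.1.

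If the power is overstated, a trial described as having four chances in five of detecting the predicted effect may have fewer than one in two. A non-significant result could then be read as evidence that 162 mg offers no advantage, when the trial could seldom have excluded the advantage the sponsor expected.

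**Working it through.** **Inputs**

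- Control rate p1 = 0.26 (section 5.1, low-dose aspirin).
- Reduction 35% (section 5.2). A 35-point absolute fall from 26% is impossible, so it is relative: p2 = 0.26 × 0.65 = 0.169, and the difference is 0.091.
- Two-sided alpha 0.05 (z = 1.960), power 80% (z = 0.8416), 1:1 allocation (section 5.2).
- The test is not named. Section 5.2 speaks of a frequency, so I compare two proportions.

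**Attempt to reproduce 128**

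Pooled-variance normal approximation, with p̄ = (p1 + p2)/2 = 0.2145:

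n per group = [1.960 × √(2p̄(1 − p̄)) + 0.8416 × √(p1(1 − p1) + p2(1 − p2))]² / (p1 − p2)²

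- √(2 × 0.2145 × 0.7855) = 0.5805, times 1.960 = 1.1378
- √(0.1924 + 0.1404) = 0.5769, times 0.8416 = 0.4856
- n = (1.6233)² / 0.091² = 2.6351 / 0.008281 = 318.2, so 319 per group

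Other formulas give 316 (unpooled), 317 (arcsine) and 340 (continuity-corrected). A one-sided test would still need 251. None is near 128.

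**Power at the planned size**

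Power = Φ{[0.091 × √n − 1.1378] / 0.5769}

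- n = 128: (1.0295 − 1.1378)/0.5769 = −0.188, power 42.6%
- n = 140 (400 × 0.7 / 2): (1.0767 − 1.1378)/0.5769 = −0.106, power 45.8%
- n = 200 (all 400 evaluable): (1.2869 − 1.1378)/0.5769 = 0.259, power 60.2%

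Exact enumeration of the Pearson chi-square test gives 42.6% at 128 per group. Fisher's exact test gives 37.1% at 128 and 40.5% at 140.

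**Other rates in the documents (pooled formula)**

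| 81 mg vs 162 mg | Source | n per group for 80% | Power at 128 | at 140 | at 200 |
|---|---|---|---|---|---|
| 26% vs 16.9% | 5.1, 35% cut | 319 | 42.6% | 45.8% | 60.2% |
| 30% vs 19.5% | 2.2, 35% cut | 264 | 49.5% | 53.0% | 68.3% |
| 20.5% vs 13.3% | 5.1 (non-pregnant), 35% cut | 428 | 33.3% | 35.9% | 48.2% |
| 30% vs 5% | 2.2, both rates | 36 | over 99.9% | over 99.9% | over 99.9% |

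The last row is a relative reduction of (30 − 5)/30 = 83%. It does not lead to 128 either.

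**What would give 128**

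- With a 35% relative reduction, the 81 mg rate would have to be about 49%, which appears nowhere in the documents.
- From 26%, the rate on 162 mg would have to fall to 12.3% (a 53% relative reduction) for 80% power at 128 per group, or to 12.8% (51%) at 140.
- A standardized difference of 0.35 between two means needs 2 × (1.960 + 0.8416)² / 0.35² = 128.1 per group. The 35% may have been entered as an effect size of 0.35. This is inference; the documents do not say so.

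**Precision**

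The expected 95% confidence interval half-width for the difference is 1.96 × √(0.3328/n): 10.0 points at 128 and 9.6 points at 140, against an assumed difference of 9.1 points.

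**Dropout**

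256 / 0.7 = 366, so 400 is more than enough to retain 256 evaluable women. It is not enough for 638 (2 × 319), which would need 638 / 0.7 = 912 enrolled.

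**The case against.** The strongest objection is that section 5.2 prints no control rate, so 43% is conditional on reading 26% across from section 5.1. The 30% in section 2.2 has a fair claim too. It concerns the same two doses, and the listed title of its source refers to high-risk pregnancy, which is closer to the eligibility criteria. The listed title of the source cited for 26% concerns obesity and platelet reactivity. From 30%, power is 49.5% at 128 and 53.0% at 140, so the statement that power is below one half fails at 140 per group. This stands as a qualification: the figure should be given as about 43% to 53% over the two pregnancy rates and 128 to 140 per group. All of these remain far below 80%. The 20.5% rate is labelled non-pregnant and is only a sensitivity check.

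Second, 128 may come from an input that was not printed, such as a standardized difference of 0.35. Section 4.7.1 evaluates the primary outcome with measured serum thromboxane levels, which are continuous. That may explain the number, but it would not rescue the sentence, which claims power for a reduction in a frequency. It does mean the fix should first ask what was used.

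Third, the interval argument must not be pushed too far. It largely restates that power is low. A non-significant result favouring 81 mg by about 1 point or more would exclude a 9.1-point benefit. The fair statement is that a non-significant result often could not exclude it.

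**Conclusion.** The concern holds. The 80% power stated for 128 women per group is not reproduced from any low-dose rate in the documents combined with the 35% reduction. On the natural reading (26% on 81 mg, 35% relative, two-sided 0.05, two proportions), the requirement is 319 per group, about 2.5 times the stated number (319/128 = 2.49). Power is 42.6% at 128 per group and 45.8% at 140. The gap is too large to be explained by the choice of formula.

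The result rests on two readings that section 5.2 leaves unstated: that 26% is the 81 mg rate and that 35% is relative. The first could be replaced by 30% without changing the conclusion. The trial is not necessarily too small: if the true effect is near the 30%-to-5% change in section 2.2, it is amply powered. The plan sizes for one effect and cites a much larger one, and does not reconcile them.

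**What to change.** 1. State in section 5.2 the control rate, the rate expected on 162 mg, whether the reduction is relative or absolute, the endpoint and the test that produced 128. If an input was used that is not printed, print it and describe the effect in those terms.
2. If the inputs are those in sections 5.1 and 5.2, restate the power. Suggested wording:

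> With 26% aspirin resistance on 81 mg and 16.9% on 162 mg (a 35% relative reduction), two-sided alpha 0.05 and [named test], 128 evaluable women per group give about 43% power and 140 per group (400 less 30%) about 46%. Power of 80% applies to a fall from 26% to about 12.3% (128 per group) or 12.8% (140 per group).

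These figures are for the chi-square test; for Fisher's exact test the first two become about 37% and 41%, and the detectable rates need recalculating.

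3. If the sponsor prefers to rely on a larger effect, justify it from the 30%-to-5% figure in section 2.2 and explain why 35% was used.
4. Check that the source cited in section 5.1 supports 26% as a rate in pregnancy.

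The allowance for dropout needs no correction as an inflation of 256, but it should not be presented as restoring 80% power for the 35% reduction.

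The cost is a rewording of section 5.2 and one source check. The stated power for a 35% reduction becomes less favourable. No patients, visits or procedures are added.
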